# f. Will it be possible to continue the more (most) appropriate therapy for the participant(s) after the conclusion of the study?

Our study is diagnostic only and will not limit the participants' treatment options. The conduct of our research should actually improve the speed with which the participants receive the most appropriate therapy, as we expect to be able to distinguish much more quickly between the differentials for the symptoms the patients experience.

## g. Study Endpoint(s)

Endpoint of these examinations is to define distinctive MR signal characteristics of osteonecrosis lesions. Secondary endpoint is to define specific ferumoxytol-MR imaging features that indicate treatment response to decompression surgery and stem cell transplant.

## **3. BACKGROUND**

#### a. Past Experimental and/or Clinical Findings

Our group has worked on MR imaging techniques with iron oxide nanoparticles since 1995. We and others have found that intravenously injected ultra small superparamagnetic iron oxide nanoparticles (USPIO) with diameters in the order of 20-50 nm cause a long lasting, enhancement on MR images. Mononuclear cells in the bone marrow, including macrophages and mesenchymal stromal cells, phagocytose USPIO which leads to a significant negative (dark) signal effect on T2-weighted MR images (1-4). This can be used for improved delineation of bone lesions and for in vivo tracking of macrophages and stem cells (1, 4). In pathologies with an increased microvascular permeability, USPIO extravasate into the interstitium and cause a T1-effect of the target tissue, which is strongly dependent on the proton content of the interstitial space (among other technical factors). We have thoroughly investigated various factors that lead to an optimized tissue T1-enhancement of USPIO. We have shown that malignant lesions in the bone marrow of patients show nearly no USPIO T1-enhancement, presumably due to their high cellularity, small intercellular space and low proton content. Inflammations, on the other hand, show a strong T1-enhancement, presumably due to the edematous, proton rich environment. These data suggest that tumors and inflammations may demonstrate differences in T1-enhancement. USPIO in the interstitium are subsequently slowly phagocytosed by macrophages and/or mesenchymal stromal cells, where they primarily cause a negative (dark) signal effect on T2-weighted MR images (11,13,18,19,24). Focal bone lesions in organs of the RES (reticulo-endothelial system) contain no or very few macrophages, thus they phagocytose few USPIO, and stand out as bright lesions. However, macrophage rich inflammations cause a marked signal loss on delayed T2weighted MR images. Thus, we have evidence from a variety of pre-clinical and clinical investigations, that bone lesions may show distinct T2-enhancement patterns on MRI.

Of note, I – the PI – have applied USPIO as MR contrast agents preclinical studies as well as in phase II and III clinical trials in adult patients (9-26). These contrast agents are

overall well tolerated and show excellent safety profiles in the majority of patients. The delivered iron dose via a typical ferumoxytol administration is in the order of 150-500 mg iron oxides (note that these are coated iron particles, not free iron), which is equivalent to or lower than the iron dose administered with one blood transfusion. USPIO are slowly metabolized in the liver and not excreted via the kidneys. Thus, they are safe to use in patients with renal insufficiencies and are not associated with any risk of nephrogenic sclerosis (a potential adverse event after injections of certain gadolinium chelates). Anaphylaxis or anaphylactoid reactions were reported in 0.2% of subjects, which is in the order of or lower compared to other MR contrast agents.

## 4. DRUGS, BIOLOGICS, REAGENTS, OR CHEMICALS USED IN THE STUDY

#### a. Investigational Drugs, Biologics, Reagents, or Chemicals

Investigational Product 1	
Name:	Feraheme™
Dosage:	5 mg Fe/kg
Administration Route:	Intravenous
Manufacturer	AMAG
IND#	111,154

### b. Commercial Drugs, Biologics, Reagents, or Chemicals

Commercial Product 1	
Name:	NA
Dosage:	NA
Administration Route	NA
New and different use? (Y/N)	NA

# 5. DISINFECTION PROCEDURES FOR MEDICAL EQUIPMENT USED ON BOTH HUMANS AND ANIMALS

N/A

## 6. **PARTICIPANT POPULATION**

## a. Planned Enrollment

(i) Target is 20 participants: 10 patients with osteonecrosis receiving ferumoxytol; 10 patients with osteonecrosis not receiving ferumoxytol
(ii) single site study; 20.
(iii) pediatric and young adult patients (8 - 40 years), male or female subjects, referred to the cancer center for assessment of an osteonecrosis lesion in the bone.
iv) control pediatric and young adult patients (8 - 40 years), male or female subjects, with osteonecrosis who receive an MRI without ferumoxytol
Inclusion criteria: Osteonecrosis
Age, Gender, and Ethnic Background:
8 to 40 years of age
any gender
any ethnicity

#### b. Vulnerable Populations

As avoiding ionizing radiation is an increasing concern in the medical field, and as ionizing radiation exams are not particularly effective in distinguishing between the two conditions, developing a safe and effective diagnostic exam for the pediatric population is highly desirable.

#### c. Rationale for Exclusion of Certain Populations

N/A

### d. Stanford Populations

N/A. While we will not avoid recruiting these populations, we will not specifically seek them out; and they would only be considered for the research if they undergo the same screening process as other participants.

#### e. Healthy Volunteers

None, N/A

## f. Recruitment Details

All potential participants will be patients seen through regular referral methods in the pediatric oncology clinic and will be offered participation if it seems appropriate. If the patient and/or parents are interested in this new experimental imaging procedure, a meeting with a pediatric radiologist from the study team will be arranged or the phone details will be provided which allows the radiologist to set up an appointment with the patient and/or parents via phone or in person. The study investigator will then explain and discuss the details of the experimental MR imaging study procedure with the patient and/or parents and discuss the possibility of enrollment of the child into the study. Recruitment will be invitation only.

#### g. Eligibility Criteria

i. Inclusion Criteria

8-40 years of age, suspected or confirmed diagnosis of osteonecrosis

ii. Exclusion Criteria

contraindication to MRI (metal implants), need for sedation or anesthesia, claustrophobia. Hemosiderosis/ hemochromatosis as defined by decreased T2-signal of liver will

exclude patients from arm 1 (ferumoxytol-MRI). Patients with hemosiderosis/hemochromatosis can still be included in the osteonecrosis study and would undergo MRI evaluation without ferumoyxtol (control group).

#### h. Screening Procedures

During the course of a normal clinic visit, collaborating pediatric oncologists who note a patient who meets the inclusion/exclusion criteria, will inform them about the opportunity to enroll in the study. If the patient and/or parents are interested, a meeting with a pediatric radiologist from the study team will be arranged or the patient's name, phone details and MRN of the patient will be provided to allow the radiologist to set up an appointment with the patient and/or parents. We have applied for a limited Waiver of Authorization for Recruitment.

## i. Participation in Multiple Protocols

During the enrollment process, patients will be asked if they are enrolled in any other studies, and a question will be on the top of the first page of the consent form. Should the patient be enrolled in another study, they will be advised to notify the PI for the other study that they are participating in our imaging study, and they will be encouraged to have the other PI contact our staff. We do not expect our study to impact any other results, as the MRI is a non-invasive imaging study; but as it involves a metabolically active drug (iron supplement), we will do our best to communicate clearly with the patients and any other PIs. Of note, the ferumoxytol dose administered for MRI (5 mg/kg) is far below the usual dose for the treatment of iron deficiency (2 x 510 mg) and does not affect the Hb levels of the patients. Should questions remain about the advisability of participation in our study, the potential participant will be excluded.

#### j. Payments to Participants

No payment, N/A

## k. Costs to Participants

No costs will be charged to the participant. We expect to pay scanning costs from an NIH grant and the PI's research startup funds, including the contrast agent costs.

## I. Planned Duration of the Study

The revised anticipated study duration is until 2026. (i) screening should take 15-30 minutes; (ii) active participation involves two MRI scans for a total of approximately 2-3 hours; (iii) follow up MRI(s) within 1-6 months after decompression surgery will be evaluated to determine clinical outcomes (iv) data analysis will continue until publication in approximately 12 months from initiation.

## 7. RISKS

## a. Potential Risks

i. Investigational devices

N/A

ii. Investigational drugs

We applied for an IND with the FDA for off-label administration of the FDA-approved iron supplement ferumoxytol as a contrast agent (IND 111 154 )

iii. Commercially available drugs, biologics, reagents or chemicals

[name] has applied USPIO as MR contrast agents in phase II and III clinical trials in adult patients. These contrast agents are generally well tolerated and show excellent safety profiles. The delivered iron dose via a typical ferumoxytol administration is in the order of 150-500 mg iron oxides (note that these are coated iron particles, not free iron), which is equivalent to or lower than the iron dose administered with one blood transfusion. USPIO are slowly metabolized in the liver and not excreted via the kidneys. Thus, they are safe to use in patients with renal insufficiencies and are not associated with any risk of nephrogenic sclerosis (a potential adverse event after injections of certain gadolinium chelates). The FDA recently issued a box warning about rare but potentially fatal allergic reactions to ferumoxytol. Anaphylaxis or anaphylactoid reactions were reported in 0.2% of subjects, which is in the order of other MR contrast agents. So far, we did not observe any allergic reaction in our patient population.

iv. Procedures

MRI w & w/o contrast f/u MRI w/o contrast

Magnetic fields do not cause harmful effects at the levels used in the MRI machine. However, the MRI scanner uses a very strong magnet that will attract some metals and affect some electronic devices.

In some cases, having those devices means the participant should be excluded. Additionally, when contrast is injected, as with any intravenous injection, there are risks of bruising, bleeding, or infection from the venipuncture; and allergic reaction to the injected contrast.

v. Radioisotopes/radiation-producing machines

N/A

vi. Physical well-being

N/A

vii. Psychological well-being

Some small risk of a patient experiencing claustrophobia. This is an infrequent but regular occurrence in any MRI facility. Every effort is made to minimize this risk and the research and clinical staff are well trained to act appropriately.

viii. Economic well-being

N/A

ix. Social well-being

N/A

x. Overall evaluation of risk

Low

### b. International Research Risk Procedures

N/A

## c. Procedures to Minimize Risk

An MRI screening form will be completed prior to participation. Any potential contraindication to MRI revealed by the comprehensive screening form will result in participant exclusion. The research team will use the clinical systems and the REDCap database for data management. REDCap is maintained by Clinical Informatics at Stanford University as a HIPAA compliant, secure, encrypted database for research purposes. Data exported by the researchers from these secure systems will only be exported in a deidentified form to minimize risks to confidentiality.

#### d. Study Conclusion

Endpoint of these examinations is to define distinctive MR signal characteristics of malignant tumors and infection/inflammatory processes, which will be immediately applicable in a clinical setting. The scans occur in the clinical setting and make use of the normal clinical procedures and precautions, including the availability of medical emergency response teams and constant monitoring by medical personnel.

#### e. Data Safety Monitoring Plan (DSMC)

i. Data and/or events subject to review

Of note, [name] has applied iron oxide nanoparticles as MR contrast agents in phase II and III clinical trials in adult patients. These contrast agents are very well tolerated and show excellent safety profiles. The delivered iron dose via a typical ferumoxytol administration is in the order of 150-500 mg iron oxides (note that these are coated iron particles, not free iron), which is equivalent to or lower than the iron dose administered with one blood transfusion. Iron oxide nanoparticles are

slowly metabolized in the liver and not excreted via the kidneys. Thus, they are safe to use in patients with renal insufficiencies and are not associated with any risk of nephrogenic sclerosis (a potential adverse event after injections of certain gadolinium chelates). Anaphylaxis or anaphylactoid reactions were reported in 0.2% of subjects, which is in the order of or lower compared to other MR contrast agents (see FDA report: Lu M, Cohen MH, Rieves D, Pazdur R. FDA report: Ferumoxytol for intravenous iron therapy in adult patients with chronic kidney disease. Am J Hematol. 2010;85(5):315-9). In the unlikely event of an anaphylactoid reaction, appropriate actions will be taken as with any other contrast agent reaction and the event will be reported to the IRB.

ii. Person(s) responsible for Data and Safety Monitoring

The Stanford Cancer Center Data and Safety Monitoring Committee (DSMC) will be the monitoring entity for this study. The DSMC will audit study-related activities approximately once per year to determine whether the study has been conducted in accordance with the protocol, local standard operating procedures, FDA regulations, and Good Clinical Practice (GCP). In addition, the DSMC will regularly review serious adverse events and protocol deviations associated with the research to ensure the protection of human subjects. Results of the DSMC audit will be communicated to the IRB and the appropriate regulatory authorities at the time of continuing review, or in an expedited fashion, as needed.

iii. Frequency of DSMB meetings

AEs will be reviewed at every research team meeting, or at least once a month, whichever is more frequent.

- iv. Specific triggers or stopping rules
- v. Any signs of an anaphylactoid reaction, such as rash, urticaria, nausea, cough, breathing difficulty will lead to discontinuation of contrast administration and symptomatic treatment. DSMB Reporting
- vi. The ME will forward written reports to the appropriate entities via email. Will the Protocol Director be the only monitoring entity? (Y/N)
  - Ν
- vii. Will a board, committee, or safety monitor be responsible for study monitoring? (Y/N)
  - Y

## f. Risks to Special Populations

## g. Risk to Children

The research presents more than minimal risk to children, but holds out the prospect of direct benefit for the individual subject or is likely to contribute to the subject's wellbeing. MRI is recognized as a non-significant risk, when used on-label, as in this research. Additionally, the contrast agent is an FDA approved medicine being used off-label, and has been assessed as having significantly similar or lower risk to existing on-label contrast agents used in similar applications. As off-label use of this contrast agent is expected to quickly and clearly illuminate an otherwise difficult diagnostic question (presence of osteonecrosis, success of osteonecrosis surgery) with low risk, no ionizing radiation, no invasive procedures (such as bone biopsy), the study team assesses this research as research involving marginally greater than minimal risk with prospect of direct benefit to the participant.

## 8. **BENEFITS**

We expect to be able to accurately delineate and differentiate bone lesions by assessing the difference in uptake and retention of the contrast agent on MRI scans. As this is a significant improvement over the existing standard of care, participants may benefit by improved diagnosis of an osteonecrosis. In patients who already have a specific diagnosis of osteonecrosis, confirmation of the existing diagnosis and better assessment of treatment effects are potential benefits. Overall, ferumoxytol can limit potentially painful and unnecessary biopsies, provide quicker and more accurate diagnoses, quicker access response to therapy, and thereby, reduce morbidity and mortality. In patients with osteonecrosis, the information obtained from ferumoxytol-enhanced MRI scans can improve prediction of successful treatment outcomes.

## 9. PRIVACY AND CONFIDENTIALITY

All participant information and specimens are handled in compliance with the Health Insurance Portability and Accountability Act (HIPAA) and privacy policies of Stanford University, Stanford Health Care, and Stanford Children's Health.

## 10. STATISTICAL PLAN

All experiments were analyzed using R version 3.4.4. The number of patients per experimental group were determined by power analyses. Signal-to-noise ratios (SNR) and T2 relaxation times were pairwise compared between osteonecrosis lesions with and ferumoxytol administration, and between decompression track areas with and without visible iron-labeled cells, using a mixed-effects model including a random effect term accounting for correlation among the measures within a same patient. A Fisher exact test was applied for comparison of clinical outcomes of osteonecrosis with and without ferumoxytol enhancement. In addition, differences in time to progression of osteonecrosis from surgery between bone lesions that did or did not enhance with ferumoxytol were assessed by log-rank tests. Because of the small sample size and exploring purpose of this study, a P < 0.05 without adjustment for multiple comparisons was considered to indicate significant differences between experimental groups.

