## **1. PURPOSE OF THE STUDY**

#### a. Brief Summary

The overarching goal of our project is to establish a novel, non-invasive, immediately clinically applicable imaging test for the diagnosis of bone tumors, including primary malignant bone tumors, metastases, as well as benign bone lesions, osteonecrosis and infection/non-cancer inflammatory processes. The purpose of this project was to evaluate imaging characteristics of osteonecrosis before and after decompression surgery with ferumoxytol-enhanced MRI. Our approach relies on the FDA-approved iron supplement drug ferumoxytol (Feraheme), which is used in patients for intravenous treatment of iron deficiency. Ferumoxytol is composed of iron oxide nanoparticles, which provide a strong T1- and T2-signal on magnetic resonance (MR) images and, thus, can be used as an MR contrast agent. Based on our extensive experience with pre-clinical and clinical imaging applications of iron oxide nanoparticles, we hypothesize that MR images after intravenous injection of ferumoxytol will improve lesion detection and characterization compared to conventional unenhanced and Gd-enhanced MRI scans.

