#### b. Objectives

 We hypothesize that MR images after intravenous injection of ferumoxytol will improve the detection of osteonecrosis lesions compared to standard MRI scans.
 We hypothesize that ferumoxytol-T2-enhancement of osteonecrotic bone lesions on MR images correlates with the quantity and distribution of healthy bone marrow cells in the lesion.

3. We hypothesize that ferumoxytol-enhanced MRI will improve evaluation of therapy success of osteonecrosis after decompression surgery.

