## e. Alternative Procedures or Courses of Treatment

The current alternative diagnostic methods are: biopsy, which is invasive, painful, and frequently inadequate; Conventional MRI without an iron nanoparticle contrast, which cannot distinguish healthy and necrotic cells in osteonecrosis; PET/CT/Xray, which add exposure to ionizing radiation. The current standard of imaging is an MRI; the addition of an iron nanoparticle contrast agent is expected to make this test more sensitive and

specific. No standard treatment will be withheld, and the standard of care diagnostic test is included in our research.

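### Objective 1 claims better lesion detection than standard MRI, but no endpoint or planned analysis measures detection or lesion-to-marrow contrast

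*Combined protocol and SAP*

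**What the plan says.** **Objective.** Section 1.b, Objective 1: "MR images after intravenous injection of ferumoxytol will improve the detection of osteonecrosis lesions compared to standard MRI scans". Section 1.a makes the wider claim that ferumoxytol MRI "will improve lesion detection and characterization compared to conventional unenhanced and Gd-enhanced MRI scans". Section 2.e adds the expectation that "the addition of an iron nanoparticle contrast agent is expected to make this test more sensitive and" specific.

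**Endpoints.** Section 2.g: the endpoint is to "define distinctive MR signal characteristics of osteonecrosis lesions"; the secondary endpoint concerns imaging features of response to decompression surgery and cell transplant. Section 7.d words the endpoint differently and for other diseases: "Endpoint of these examinations is to define distinctive MR signal characteristics of malignant tumors and infection/inflammatory processes".

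**Analyses.** Section 10 has lesion SNR and T2 relaxation times "pairwise compared between osteonecrosis lesions with and ferumoxytol administration", in a mixed-effects model with a patient random effect. The same model compares decompression track areas with and without visible labelled cells. A Fisher exact test on clinical outcomes and a log-rank test on time to progression complete the list.

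**Mechanism.** Section 3.a says that particle uptake by marrow cells "leads to a significant negative (dark) signal effect on T2-weighted MR images", and then: "This can be used for improved delineation of bone lesions". It adds that focal lesions with few macrophages take up little agent and appear bright.

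**The concern.** Whether a lesion is detected depends on whether it is found, or at least on how far it stands out from the tissue around it. The plan measures signal inside the lesion. A reader who follows it exactly ends with no result for Objective 1, or is left to infer one from lesion signal, which need not move in step with visibility.

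This matters because improved diagnosis is part of the stated case for the study. Section 8 lists it as a benefit, and the section on risk to children relies partly on the agent clarifying whether osteonecrosis is present.

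**Working it through.** The check is mainly a side-by-side reading.

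**1. Each endpoint and analysis against Objective 1.**

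| Item | What it measures | Detection or lesion-to-marrow contrast? |
|---|---|---|
| Endpoint, section 2.g | Lesion signal characteristics | Not named |
| Secondary endpoint, section 2.g | Features of treatment response | No |
| Endpoint, section 7.d | Signal characteristics of other diseases | No |
| Section 10, analysis 1 | Lesion SNR and T2, with v (as read) without ferumoxytol | No; marrow is not a comparator |
| Section 10, analysis 2 | SNR and T2 in decompression tracks | No |
| Section 10, analysis 3 | Clinical outcomes, Fisher exact test | No |
| Section 10, analysis 4 | Time to progression, log-rank test | No |

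**2. Is a measure supplied elsewhere?** I found none. No section defines a detected lesion, a lesion count, a reader score, sensitivity or specificity, or a contrast measure. Tissue samples (section 2.a) are examined only when available, for cell types and possibly iron; they are not named as a reference standard for detection.

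**3. Where the break lies.** Section 10 analyses lesion signal, as section 2.g asks. The step that fails is from section 1.b to section 2.g, and section 10 inherits it.

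**4. Why lesion signal cannot stand in for contrast.** Let L be lesion signal and M marrow signal on the same T2-weighted image. Contrast is C = L − M, so change in C = change in L − change in M. The lesion analysis sees only the change in L. With invented values:

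| Case | L before → after | M before → after | Change in L | C before → after |
|---|---|---|---|---|
| Marrow alone darkens | 20 → 20 | 15 → 8 | 0 | 5 → 12 |
| Both darken by 15 − 8 = 7 | 20 → 13 | 15 → 8 | −7 | 5 → 5 |
| Lesion starts darker, marrow alone darkens | 8 → 8 | 15 → 8 | 0 | −7 → 0 |

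In the first case the lesion test has nothing to find although contrast more than doubles. In the second it has a difference to find although contrast is unchanged. Objective 2, which ties lesion enhancement to healthy marrow cells inside the lesion, makes the second case conceivable. In the third, the signed contrast rises by 7 while the visible difference disappears, so a signed change needs its direction and size reported with it.

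**5. Why the absolute difference alone is not the answer.** Assumed for illustration: 10 v 10, one value per patient, t-test at two-sided 0.05, equal lesion and marrow SDs, lesion-marrow correlation 0 to 0.5. Let the lesion start 1 SD darker than marrow, marrow fall by 1.5 SD and the lesion by 0.1 × 1.5 = 0.15 SD. Mean contrast goes from −1.0 to −1.0 − 0.15 + 1.5 = +0.35 SD, so its size shrinks from 1.0 to 0.35. A simulated test on |L − M| reports that loss in only 7 to 15% of trials. These inputs are mine, and the finding does not depend on them.

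**6. The plan's own figure.** Section 6.a plans 10 patients per group, and section 10 attributes group size to power analyses. No effect size, SD, rate or power is stated, so the figure cannot be reproduced or tied to detection.

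**The case against.** The strongest reply is that the plan is consistent where it counts: the section 10 comparison serves the section 2.g endpoint. That stands. A reader might infer that the quoted comparison is itself wrong, or that its missing word matters. Neither follows: the comparison fits its endpoint, and the omission looks like a slip.

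Second, the uptake mechanism in section 3.a is described for focal bone lesions generally. That also stands. A reader might infer that the lesion test will mislead in osteonecrosis; the documents show only that it could.

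Third, the study calls itself exploratory, plans 20 patients, and enrols people whose osteonecrosis is already suspected or confirmed, so it has little scope to test detection. This limits the consequence and favours restating the objective. It does not supply the missing measure.

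Fourth, no planned analysis claims a detection result. That is correct: inference from lesion signal is a risk in interpretation, not something section 10 states. Likewise, greater sensitivity and specificity in section 2.e is an expectation in a passage on alternatives, not an endpoint left unanalysed.

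Finally, the section 2.g wording is broad enough to hold a contrast measure. But none is named there, and section 10 analyses none.

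**Conclusion.** The point holds as a mismatch between objective and endpoint. Objective 1, one of three, has no measure in either endpoint statement or in any of the four analyses. The lesion SNR and T2 comparison remains valid for describing lesion signal, but neither a significant nor a null result there would answer Objective 1.

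The finding rests on the text alone, plus reading the quoted sentence as with and without ferumoxytol. It has no numerical size: detection rates, effect sizes and SDs are not given, so any power percentage is illustration on assumed inputs and carries no weight here. It is worth fixing because the correction is cheap. It does not invalidate the other analyses.

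**What to change.** Choose one of two routes.

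**(a) Restate Objective 1** as a description of lesion signal characteristics with and without ferumoxytol, and align sections 1.a and 7.d with it. This closes the gap fully and costs only wording.

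**(b) Add one exploratory outcome to sections 2.g and 10:** lesion-to-normal-marrow contrast, as the SNR difference on the same T2-weighted image, with the T2 relaxation time difference alongside.

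- Use the existing mixed model with the patient random effect. Section 2.a allows imaging directly after injection, 1-2 days later, or both; name one of these in advance as the Objective 1 test. Enter precontrast images, where they exist, as same-patient measurements without ferumoxytol.
- Report the signed difference with its size and direction in each condition, so that a shift towards zero is not read as a gain. Do not rely on the absolute difference alone.
- Describe the result as lesion conspicuity, not sensitivity or specificity, and against unenhanced MRI only unless Gd-enhanced images exist.
- Label it post hoc if it is added after data were seen; section 10 is written in the past tense.
- Optionally, repeat the comparison without controls who have hemosiderosis or hemochromatosis (section 6.g), since marrow iron could alter their contrast.

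Route (b) costs one extra marrow region per image and one more unadjusted exploratory test. Precontrast scans may be few. Contrast is only a surrogate for detection, so this route narrows the gap without closing it.

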## 2. STUDY PROCEDURES

#### a. Procedures

Screening will occur during a regular clinic visit. Each participant will undergo an MRI after a single intravenous injection of ferumoxytol at a dose of 5 mg Fe/kg body weight. Precontrast images will be added when feasible. Postcontrast images will be obtained directly after and/or 1-2 days after ferumoxytol administration. In patients with osteonecrosis who undergo a surgical decompression procedure with implantation of bone marrow derived cells into the osteonecrosis, a ferumoxytol-enhanced MRI will be performed before surgery and follow up MR scans will be obtained at 1-6 months after the surgery. When available, routinely obtained biopsy and/or surgical resection samples of bone lesions will be examined by our collaborating pathologist for presence of mesenchymal stromal cells, macrophages and possibly iron content in samples that happen to be obtained shortly after the ferumoxytol injection.

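### Section 10 does not say how visible iron was judged in track areas; if it was read from the MR signal, the SNR and T2 P-values there are too small

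*Combined protocol and SAP*

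**What the plan says.** Section 10 sets up two signal comparisons. The first is by ferumoxytol administration: "Signal-to-noise ratios (SNR) and T2 relaxation times were pairwise compared between osteonecrosis lesions". The second, at issue here, is "between decompression track areas with and without visible iron-labeled cells, using a mixed-effects model", with a random effect for correlation within a patient. The decision rule for both is that "a P < 0.05 without adjustment for multiple comparisons was considered to indicate significant differences between experimental groups".

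No section defines *visible*. The plan names no sequence, time point, reader, threshold or reference standard for it.

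Two other sections bear on the likely meaning. Section 3.a says that mononuclear marrow cells "phagocytose USPIO which leads to a significant negative (dark) signal effect on T2-weighted MR images", and adds: "This can be used for improved delineation of bone lesions and for in vivo tracking of macrophages and stem cells". Section 2.a mentions pathology of routine samples when these exist, including "possibly iron content in samples that happen to be obtained shortly after the ferumoxytol injection". Section 10 does not connect those samples to the grouping of track areas.

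The secondary endpoint in Section 2.g is to "define specific ferumoxytol-MR imaging features that indicate treatment response to decompression surgery and stem cell transplant".

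**The concern.** A significance test assumes that group membership was not decided by the outcome. If a reader calls an area visible because it looks dark, and the same darkness is then measured as T2 or SNR, the two groups differ by construction. A small P-value would then largely restate that areas called dark measure darker. It would not show that labelled cells are present.

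The random effect does not help. It removes the level that a patient's areas share, whereas the selection acts on differences between areas, including those within one patient.

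This is the only track-level comparison in Section 10. A reader interested in the transplant part of the secondary endpoint could take its P-value as evidence that MRI detects the transplanted cells.

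**Working it through.** **Step 1: what the documents supply.** The nominal level is 0.05 (Section 10; two-sided assumed). The target is 10 patients with and 10 without ferumoxytol (Section 6.a). The documents do not give the number of patients with decompression, the number of track areas per patient, how closely the visibility call follows the measured signal, or the share of signal variation that lies between patients. The plan gives no figure for this contrast, so there is none to reproduce. Everything below rests on assumed inputs and serves to show direction and range.

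**Step 2: model under the null (no iron anywhere).** For area j of patient i, with total SD 1:

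- T2(ij) = √ICC · u(i) + √(1 − ICC) · e(ij)
- visual score(ij) = r · T2(ij) + √(1 − r²) · z(ij)

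Here u, e and z are independent standard normal, ICC is the between-patient share of variance, and r is the correlation of the visual score with measured T2. The half of each patient's areas with the lowest scores is labelled visible. With d(i) the visible minus not-visible mean for patient i, the test is t = mean(d) / (SD(d)/√n) on n − 1 degrees of freedom.

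**Step 3: the artefact in closed form, two areas per patient.** The within-patient correlation of score and T2 is w = r√(1 − ICC) / √(r²(1 − ICC) + 1 − r²). The expected difference created by sorting alone is −w · √(1 − ICC) · 2/√π, where 2/√π = 1.128. For r = 0.5:

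- ICC 0: w = 0.500; 0.500 × 1.000 × 1.128 = 0.56 SD
- ICC 0.5: w = 0.354/0.935 = 0.378; 0.378 × 0.707 × 1.128 = 0.30 SD
- ICC 0.8: w = 0.224/0.894 = 0.250; 0.250 × 0.447 × 1.128 = 0.13 SD

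At r = 0 the difference is zero. The direction therefore follows without simulation.

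**Step 4: rejection rate at nominal 5%, r = 0.5** (10,000 replicates per cell; a repeat with 20,000 agrees to within about 1 point).

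| Patients | Areas per patient | ICC 0 | ICC 0.5 | ICC 0.8 |
|---|---|---|---|---|
| 10 | 2 | 23% | 14% | 9% |
| 10 | 4 | 53% | 32% | 16% |
| 5 | 2 | 12% | 9% | 6% |
| 5 | 4 | 24% | 15% | 9% |

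With r = 0 every cell is about 5%. With r = 0.9, 10 patients and four areas, the rate is 99% at ICC 0.5 and 86% at ICC 0.8.

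**Step 5: does the planned model repair it?** A random-intercept REML model on the same data (10 patients, r = 0.5, ICC 0/0.5/0.8) rejects in 25/14/9% of runs with two areas and 60/36/18% with four. At r = 0 it gives 5–6%. The patient term does not remove the inflation.

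**Step 6: does it reach SNR?** Suppose SNR is measured on a separate image (10 patients, four areas, ICC 0.5, r = 0.5). If its area-level deviation is unrelated to that of T2, rejection is 5%. At a correlation of 0.6 it is about 15%, and at 1 it is 32%. SNR is affected only if it shares the images used for the call or moves with the signal used for it.

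**Step 7: sensitivity to the labelling rule.** These runs use the random-intercept model, 10 patients, four areas and r = 0.5. One cut-off across all patients, at the median score, gives 75/55/28% at ICC 0/0.5/0.8. A strict reader who calls 1–10% of iron-free areas visible gives 2–30% at ICC 0.5 and 1–14% at ICC 0.8. The low ends fall below 5% because two visible areas seldom occur, and such runs were counted as non-rejections.

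**The case against.** The strongest reply is that the premise is not in the documents. Nothing states that visibility was read from the images that supplied SNR and T2. A reader might infer that Section 10 contains a proven circular test. The text does not support that: it leaves a definition open and makes one reading likely. That part of the reply stands, and it is why the conclusion is conditional.

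A second reply is that the split may largely follow dosing, because cells in patients without ferumoxytol would carry no ferumoxytol label. The documents do not exclude this, but the word *visible* and the separate lesion comparison by administration weigh against it.

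A third is that the size is unknown. This stands too. A reader might take one of the high percentages as this study's false-positive rate, but every input behind it is assumed, and the range runs from no inflation to near-certain rejection. Half of all areas called visible when no iron is present is also a generous assumption.

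A fourth is that the study is exploratory. Section 10 uses that to justify "without adjustment for multiple comparisons was considered to indicate significant differences between experimental groups". It limits how much one contrast can matter, but it does not make a P-value from outcome-defined groups interpretable. Nor would blinding the reader alone cure the selection, since a blinded reader still sees the dark signal.

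**Conclusion.** The point holds as a conditional one. Section 10 leaves the grouping variable of a significance test undefined, and its likeliest meaning, an MR reading, would group areas on the outcome being tested. In that case the P-value for T2 is too small, as is the one for SNR where it shares the images or moves with the signal, and the random effect does not correct it. If the label came from a source independent of the measured signal, the test keeps its nominal level and the point falls away.

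Only the direction is firm. The illustrative range of about 6% to 53% rests on r = 0.5, half of each patient's areas called visible, 5 or 10 patients, two or four areas, ICC from 0 to 0.8, and the paired test.

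A reader might extend the criticism to the rest of Section 10. That is not supported. The lesion comparison is grouped by ferumoxytol administration, and the Fisher and log-rank tests have clinical outcome and time to progression as outcomes, not the signal that forms the groups. Severity is minor: one exploratory contrast, and a cheap improvement.

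**What to change.** In Section 10:

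1. State how *visible* was judged: sequence, time point, reader, and any reference other than MR.
2. For T2, and for SNR where it applies, if the outcome was measured on the images used for the visibility call or is expected to move with the signal used for it, report visible and not-visible areas descriptively. Give estimates and the numbers of areas and of patients, with no P-value or claim of significance. State that the contrast does not test for the presence of labelled cells.
3. Keep the mixed-model test only where the label is independent of the measured signal, for example from histology, and name that reference.

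The cost is wording, with no new data. At most two exploratory P-values are lost, one for T2 and one for SNR.
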